4.3 Suspension of enrollment

Adverse events and serious adverse events (SAEs) are expected to occur frequently in this study based on the patient population being accrued and the nature of the advanced malignancy. As a result, there is no specific incidence rate of SAEs that will define a stopping rule. Instead, regular systematic review of SAEs will serve as the basis for enrolment suspension or prematurely stopping of the study.

4.3.1 Criteria for suspension of enrollment

In any case, the study will be paused and the Investigators, Institutional Review Board (IRB)/Independent Ethics Committee (IEC), regulatory agencies, and SRC will be promptly informed if any patient develops, in the dose expansion parts (Part 1 and Part 3), any of the following events assessed to be related to study drug by the Investigator and/or SRC:

- Life-threatening (Grade 4) toxicity that is unexpected and/or unmanageable (ie, does not resolve to Grade 3 or lower within 7 days)
- Death

The SRC will be urgently convened to review the safety data and make recommendations for potential changes in the study conduct (e.g. permanent discontinuation, dose reduction of a treatment in the combination arm or adaptation of the safety monitoring measures). If enrollment suspension is triggered due to an AE suspected to be related to ANV419, the enrollment in the

study will be paused. However, if the enrollment suspension is triggered due to a known toxicity of pembrolizumab or ipilimumab, or suspected synergistic toxicity in only one of the tested combination therapy arm, the monotherapy arm and the other combination therapy arm will still proceed if toxicity is not observed.

Should enrollment in the study or in one treatment arm be suspended, the study will not be restarted until all parties (SRC and Sponsor) have agreed to the course of action to be taken and the IRBs/IECs have been notified.

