- 2 responses in 3 to 7 patients;
- 3 responses in 8 to 13 patients;
- 4 responses in 14 to 19 patients; or
- 5 responses in 20 to 27 patients.

Response (complete response [CR] or partial response [PR]) will be assessed at each disease evaluation by the Investigator.

Part 2: Combination Dose Finding

This part will only be initiated following approval of a substantial amendment supporting the ANV419 starting dose in the combination part. The submission will include data from ANV419-001 Study and from Part 1 of this trial, and occur at any time when at least 2 responses have been observed in the Monotherapy Dose Expansion part. The Combination Dose Finding part will be comprised of 2 arms (Arms B and C) that will identify a recommended Phase 2 dose (RP2D) for ANV419 in each arm when administered in combination with pembrolizumab (Arm B) or ipilimumab (Arm C) at the prescribed dosing. The number of patients recruited to each arm will be between 6 and 25 patients depending on the number of dose increments possible. A minimum of 6 patients will be treated at RP2D. The patients from the Combination Dose Finding part will not be randomized into the Combination Dose Expansion part.

Dosing of ANV419 when administered in combination with pembrolizumab (Arm B) or ipilimumab (Arm C) will occur as shown in Table TS5, with a dose of ANV419 currently planned to start at Patients in the Combination Dose Finding part will be treated with a minimum of 24 hours interval between patients to allow for monitoring of acute toxicities. Dose level 1, as shown in Table TS5, will be reviewed by the Safety Review Committee

a. Thall PF, Simon R. Practical Bayesian guidelines for phase IIB clinical trials. Biometrics. 1994;50(2):337-349.

(SRC) per the safety evaluations and the SRC will make dose increment recommendations at each dose level, not exceeding 3-fold increment from one dose level to the next. The maximum dose level explored will not exceed the Q3W dose of ANV419 monotherapy studied in the ongoing ANV419-001 study. The dose-limiting toxicity (DLT) period for the Combination Dose Finding part will last for

Example 2. For details on the DLT criteria for the Combination Dose Finding part of this study, see the section below labeled "Dose-limiting toxicity criteria (applicable to Combination Dose Finding part only)."

Table TS5. ANV419 Dose Escalation Plan for Combination Dose Finding Part (Pembrolizumab or Ipilimumab)

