3.1.4 Dose-Limiting Toxicity Criteria (Applicable to Combination Dose Finding Part Only)
A DLT is defined as any of the treatment-emergent AEs (TEAEs) listed below, as defined by the National Cancer Institute Common Terminology Criteria for Adverse Events (NCI CTCAE) version 5.0, occurring during the DLT period (
DLT definitions are the following:
DL1 definitions are the following.

An SRC will be convened, comprised of enrolling study Investigators, Medical Monitor, and the Sponsor Medical Director or designee. All potentials DLTs will be reviewed by the SRC for a final determination and for the SRC to make recommendations regarding the study. The SRC will also

consider AEs, particularly high-grade toxicities that may have occurred in patients in any treatment arm (even beyond the DLT period), when making decisions/recommendations to proceed with the study. The SRC will provide recommendations for study drug dosing and alternative dosing regimens as appropriate, not exceeding a 3-fold increment from one dose level to the next. The maximum dose level explored will not exceed the dose of ANV419 monotherapy studied in the ongoing ANV419-001 study. Near the end of dose escalation, the statistician will also contribute to dose escalation recommendation, using the BOIN design, to select the MTD/RP2D.

After completion of the DLT period for each cohort, intra-patient dose escalation is permitted with approval of the Investigator and provided the following criteria have been met:

- The patient has completed at least 1 treatment cycle;
- The DLT assessment of the dose level to which the patient will be dose-escalated is complete and determined to be safe by the SRC;
- The patient did not experience any AEs related to study drug(s) >Grade 1 at the dose level prior to escalation; and
- The patient has not required any dose reduction.

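### The mandatory pause after one related death or serious Grade 4 toxicity (Protocol 4.3.1) is worded for Parts 1 and 3 only; for Part 2 events after the DLT period, no readable rule holds new patients until the safety committee has reviewed

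*Protocol*

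**What the plan says.** Protocol 4.3.1 sets a single-event trigger. The study is paused, and investigators, ethics committees, regulators and the SRC are informed, on a trigger whose scope reads "in the dose expansion parts (Part 1 and Part 3), any of the following events assessed to be related to study drug". The listed events are death, and Grade 4 toxicity that is unexpected and/or fails to settle to Grade 3 or lower within 7 days. Then "The SRC will be urgently convened to review the safety data". The same section has a restart condition with no part limit: "Should enrollment in the study or in one treatment arm be suspended, the study will not be restarted until all parties" have agreed. It also has wording for "suspected synergistic toxicity in only one of the tested combination therapy arm", under which the other arms may go on.

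Part 2 has its own safeguards:

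- Patients "will be treated with a minimum of 24 hours interval between patients to allow for monitoring of acute toxicities" (Synopsis, Part 2).
- Each patient is observed for 23 hours in Cycles 1 and 2 (5.4.3.2).
- Dose assignment follows the Bayesian optimal interval (BOIN) rules cohort by cohort (3.1.2.1), and the SRC makes a dose recommendation at each level (Synopsis).
- "All potentials DLTs will be reviewed by the SRC for a final determination" (3.1.4).
- The SRC also weighs high-grade toxicity in any arm, "even beyond the DLT period), when making decisions/recommendations to proceed with the study" (3.1.4).

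Across all parts, section 4.3 gives no SAE rate as a stopping rule and says instead that "regular systematic review of SAEs will serve as the basis for enrolment suspension or prematurely stopping of the study".

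**The concern.** A rule that acts on one catastrophic related event does a different job from BOIN. BOIN picks the next dose from observed DLT rates against a 25% target. The 4.3.1 rule stops intake first and asks questions afterwards. Part 2 is where an unforeseen interaction between ANV419 and a checkpoint inhibitor would first appear in this protocol, yet the trigger does not reach it.

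Late events are foreseeable. Sections 5.4.5 and 5.4.5.4 warn that immune-related events may arise months after the last dose, and 5.4.5.4 adds that attributing an event to one component will be hard. At stake is whether, after a related death outside the DLT period in Part 2, the next patient waits for the SRC by rule or only if someone decides to suspend.

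**Working it through.** The plan states no figure to reproduce here, so the check sets the provisions side by side. The question for each is whether it holds new Part 2 patients, by rule, after one related death or one related unexpected and/or unmanageable Grade 4 event.

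1. **Protocol 4.3.1, trigger.** Mandatory, but only where the event occurs in Part 1 or Part 3. The limit is on where the event occurs: a Part 1 or Part 3 event attributed to ANV419 pauses enrolment in the whole study.
2. **Protocol 4.3.1, restart condition.** Covers any suspension, including one in Part 2, but does not start one.
3. **Protocol 3.2, Stopping Rules.** Concerns individual patients only.
4. **Protocol 4.3.** Covers every part, through systematic SAE review. No single-event trigger.
5. **Protocol 4.5.** Covers every part and is worded as mandatory termination, but someone must first judge the risk unacceptable or the toxicity relevant. It ends the study; it is not a hold pending review.
6. **Protocol 7.3 and 7.5.** SAEs go to the safety desk within 24 hours, and fatal or life-threatening unexpected reactions to authorities within 7 days. This is reporting, not a pause.
7. **SAP section 4.** The SRC reviews safety data on an ongoing basis. No hold.
8. **Protocol 3.1.2.1 and 3.1.4, inside the DLT period.** DLT adjudication and BOIN apply. The DLT list and period, the cut-offs, Table 6, Figure 4 and the stopping rule mentioned in step 3 cannot be read. Whether a hold exists is therefore undetermined.
9. **Protocol 3.1.4, after the DLT period.** The SRC considers the event when it makes decisions. The readable text does not say that dosing of new patients waits for this.

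Only item 9 leaves a gap that can be stated from readable text.

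Scale of the part outside the trigger: sections 3.1 and 3.1.2 give 6 to 25 patients per arm, two arms, and 130 patients in total.

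- Minimum: 2 × 6 = 12 patients.
- Maximum: 2 × 25 = 50 patients.
- Share: 50 / 130 = 0.38, so at most 38% of the planned total.

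This is the size of Part 2, not the number of patients put at risk by the wording.

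**The case against.** The strongest reply is that Part 2 is the most closely supervised part of the trial. It has staggered dosing, overnight observation, SRC adjudication of every potential DLT and an SRC recommendation at each dose level. The expansion parts have no DLT or BOIN mechanism, which plausibly explains why they alone received an event trigger. The relevant Part 2 rules are largely redacted, the SRC Charter (3.3) is not in the file, and redacted text is not absent text. Nor is the 4.3.1 pause free of judgement, since the investigator and/or SRC must first call the event related.

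Most of this stands, and it rules out three stronger readings.

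- A reader might infer that Part 2 has no protection against a single catastrophic event. The safeguards above contradict that.
- A reader might infer that the remaining patients of a cohort would be dosed regardless after an event in the first patient. That cannot be established, because the rules governing this are unreadable; acute events are also what the 24-hour spacing and 23-hour observation address.
- A reader might count every unfilled slot in an arm as exposed. That does not measure the gap: at most 9 patients may be treated at one dose level, and the SRC steps in at each level.

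What the reply does not answer is the late event. DLT adjudication and BOIN work on events in the DLT period. Outside it, the readable text offers consideration and discretion where 4.3.1 offers a pause.

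**Conclusion.** The point holds in a limited form. On the readable text, one related death or qualifying Grade 4 toxicity stops enrolment by rule in Parts 1 and 3, while in Part 2 after the DLT period it leads to reporting and SRC consideration. The SRC or sponsor can suspend, and probably would; the text does not require it before the next new patient is dosed.

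The conclusion assumes that neither the redacted Part 2 rules nor the SRC Charter already contains such a hold, so confidence is medium. No count of affected patients is offered, since none can be derived. This is a cheap safety improvement, not a flaw in the analysis. SAP sections 1 and 5 record that the trial stopped after Part 1 with no responses, so no reported data are affected; the point matters only if Part 2 is opened or the design reused.

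**What to change.** In Protocol 4.3.1, replace the words confining the trigger to the two expansion parts with *in any part of the study*. In 3.1.2.1, add one sentence: *the pause and SRC review under 4.3.1 come before any further new Part 2 patient is dosed*. The existing wording on toxicity confined to one combination arm can decide whether one or both arms hold, and the existing restart condition applies unchanged. If a redacted rule or the SRC Charter already does this, a cross-reference from 4.3.1 is enough.

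Section 3.1.2 requires a substantial amendment before Part 2 can open, so both changes fit there. They use the existing committee and criteria. The cost is possible short enrolment pauses in Part 2.

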4.4 Discontinuation of study treatment

Discontinuation of a patient from study treatment may occur or any of the following reasons:

- The patient or legal representative (such as a parent or legal guardian) withdraws consent;
- Confirmed radiographic disease progression;

Note: A patient may be granted an exception to continue on treatment with confirmed radiographic disease progression if clinically stable or clinically improved. Such cases should be discussed by the Investigator or treating physician with the Sponsor.

Note: In certain circumstances, a patient experiencing disease progression per RECIST without clinical deterioration may be allowed to continue on treatment if the Investigator considers it in the patient's best interest and in agreement between the Investigator and Sponsor. If repeated tumor assessment within 4 to 8 weeks confirms progressive disease, the patient will need to be discontinued permanently from treatment.

- Occurrence of any medical condition or circumstance that exposes the patient to substantial risk and/or does not allow the patient to adhere to the requirements of the Protocol;
- Any SAE, clinically significant AE, DLT, severe laboratory abnormality, intercurrent illness, or other medical condition which indicates to the Investigator that continued participation is not in the best interest of the patient;
- Patients who meet Hy's law will be discontinued from treatment;
- Pregnancy;
- Requirement of prohibited concomitant medication;
- Patient failure to comply with Protocol requirements or study-related procedures;
- The patient is lost to follow-up; or
- Termination of the study by the Sponsor or the regulatory authority.

Patients who discontinue for reasons noted above other than progressive disease will have post-treatment follow-up for disease status until disease progression, initiation of a non-study cancer treatment, withdrawal of consent, or lost to follow-up. In addition, each patient, irrespective of disease progression, will be followed for survival by telephone (or public records when allowed as per local regulation) until death or study termination whichever occurs first. Study staff should make every effort to complete the full panel of assessments scheduled for the End of Study Visit in addition to disease evaluation as noted above (■■■ OR ≤30 days since last

dose of study drug). The reason for patient withdrawal must be documented in the electronic case report form (eCRF).

In the case of patients lost to follow-up, attempts to contact the patient must be made and documented in the patient's medical records.

Any patient in the Combination Dose Finding part that does not complete the DLT period for reason other than DLT or that is not DLT evaluable will be replaced.

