Grade 2 Asymptomatic (AST or ALT > 3.0 to ≤ 5.0 × ULN and/or total bilirubin > 1.5 to ≤ 3.0 × ULN) Grade 3 AST or ALT 5.0-20.0 × ULN and/or total bilirubin 3-10 × ULN, OR symptomatic liver dysfunction; fibrosis by biopsy; compensated cirrhosis; and reactivation of chronic hepatitis	 Stop unnecessary medication and any potential hepatotoxic drugs Consider administration of steroids if no improvement in 3-5 days Increase monitoring frequency to every 3 days Consider adding mycophenolate mofetil if no improvement after 3 days Consider hepatology consult for Grade 2 and above Start steroids 1-2 mg/kg methylprednisolone or equivalents Consider liver biopsy Monitor labs daily 	Withhold ANV419 until ≤ Grade 1; continue at same dose Permanently discontinue ANV419
Grade 4 AST or ALT > 20.0 × ULN and/or total bilirubin > 10 × ULN OR decompensated liver function	Consider adding methylprednisolone 2 mg/kg/d equivalents	Permanently discontinue ANV419

Note: Combination of AEs suggestive of drug induced liver injury (DILI), with hepatocellular injury (AST or ALT $> 3.0 \times ULN$) accompanied by evidence of impaired hepatic function (total bilirubin elevation $> 2 \times ULN$), in the absence of evidence of initial biliary obstruction (i.e., significant elevation of ALP) or some other explanation of the injury (e.g., viral hepatitis, alcohol hepatitis), see FDA guidance, should lead to permanent discontinuation from treatment.

Other adverse events

For other adverse events deemed as clinically significant and for which no specific guidelines are provided, the following dose modifications should be followed (Table 16).

Table 16: Management guidelines for "other" ANV419 related adverse events

CTCAE v5.0	Dose modification
Grade 1	Continue at the same dose of ANV419
Grade 2	If tolerable: Continue at the same dose of ANV419;
	If intolerable: withhold ANV419 until \leq Grade 1 or baseline;
	reinstate ANV419 at the same dose
Grade 3	Withhold ANV419 until ≤ Grade 1 or baseline;
	1 st occurrence: reinstate ANV419 at the same dose
	2 nd occurrence or if not manageable: permanently discontinue if
	3rd occurrence: permanently discontinue ANV419
Grade 4	Permanently discontinue ANV419

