5.4.5.4 Management of adverse events in combination arms

AEs associated with pembrolizumab or ipilimumab exposure may represent an immunologic etiology. These irAEs may occur shortly after the first dose or several months after the last dose of pembrolizumab/ipilimumab treatment and may affect more than 1 body system simultaneously. Therefore, early recognition and initiation of treatment is critical to reduce complications. Based on existing clinical study data, most irAEs were reversible and could be managed with interruptions of pembrolizumab or ipilimumab, administration of corticosteroids, and/or other supportive care. For suspected irAEs, ensure adequate evaluation to confirm etiology or exclude other causes. Additional procedures or tests such as bronchoscopy, endoscopy, or skin biopsy may be included as part of the evaluation. Based on the severity of irAEs, withhold or permanently discontinue pembrolizumab/ipilimumab, and administer corticosteroids. Consultation with disease-specific specialists should be considered. Dose modification and toxicity management guidelines for irAEs associated with pembrolizumab and ipilimumab are provided in Table 18 and Table 19, respectively.

Attribution of toxicity and holding study drugs

When study drugs are administered in combination, attribution of an AE to a single component is likely to be difficult. Therefore, while the Investigator may attribute a toxicity event to the combination, to ANV419 alone, to pembrolizumab alone, or to ipilimumab alone, for AEs listed in Table 18 and Table 19, both interventions must be held according to the criteria in Table 18 and Table 19.

For AEs that occur with the combination of ANV419 and pembrolizumab or ANV419 and ipilimumab that clearly can be attributed to ANV419, please refer to Section 5.4.5 for management guidelines and recommended dose modifications to be taken for ANV419.

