Diarrhea/colitis	Grade 2 or 3 Recurrent Grade 3 or Grade 4	Withhold. Upon resolution to ≤Grade 1, may resume study treatment. Permanently discontinue.	Withhold. Upon resolution to ≤Grade 1, may resume study treatment. Permanently discontinue.	Administer corticosteroids (initial dose of 1 to 2 mg/kg prednisone or equivalent) followed by taper.	imaging. Monitor participants for continuing signs and symptoms of enterocolitis (ie, diarrhea, abdominal pain, blood or mucus in stool with or without fever) and of bowel perforation (ie, peritoneal signs and ileus). Participants with ≥Grade 2 diarrhea suspected colitis should consider GI consultation and performing endoscopy to rule out colitis. Participants with diarrhea/colitis should be advised to drink liberal quantities of clear fluids. If sufficient oral fluid intake is not feasible, fluid and electrolytes should be substituted via IV infusion.

Table 18. Dose Modification for ANV419 in Combination With Pembrolizumab (Continued)

	G 1		I		
	Grade (NCI CTCAE	Action with	Action with	Corticosteroid and/or Other	Monitoring and
irAEs	Version 5.0)	ANV419	Pembrolizumab	Therapies	Follow-Up
AST or ALT elevation or increased bilirubin	Grade 2 ⁰	Withhold. Upon resolution to ≤Grade 1, may resume study treatment.	Withhold. Upon resolution to ≤Grade 1, may resume study treatment.	Administer corticosteroids (initial dose of 0.5 to 1 mg/kg prednisone or equivalent) followed by taper.	Monitor with liver function tests (consider weekly or more frequently until
	Grade 3 ⁰ or 4 ⁰	Permanently discontinue.	Permanently discontinue.	Administer corticosteroids (initial dose of 1 to 2 mg/kg prednisone or equivalent) followed by taper.	liver enzyme value returned to baseline or is stable).
T1DM or hyperglycemia	New onset T1DM or Grade 3 or 4 hyperglycemia associated with evidence of β-cell failure	Withhold. Upon resolution to ≤Grade 1, may resume study treatment.	Withhold. ⁰	Initiate insulin replacement therapy for participants with T1DM. Administer antihyperglycemic in participants with hyperglycemia.	Monitor participants for hyperglycemia or other signs and symptoms of diabetes.

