Pneumonitis	Grade 2 Recurrent Grade 2, Grade 3 or 4	Withhold. Upon resolution to ≤Grade 1, may resume study treatment. Withhold study treatment. Upon resolution to ≤Grade 1, may resume study treatment 1 dose level lower.	Withhold. Upon resolution to ≤Grade 1, may resume study treatment. Permanently discontinue.	Administer corticosteroids (initial dose of 1 to 2 mg/kg prednisone or equivalent) followed by taper. Add prophylactic antibiotics for opportunistic infections.	Monitor participants for continuing signs and symptoms of pneumonitis. Evaluate participants with radiographic imaging.

Table 19. Dose Modification for ANV419 in Combination With Ipilimumab (Continued)

Table 19. Dose	Modification 10	or AN V 419 in	Combination V	Vith Ipilimumab	(Continuea)
irAEs Diarrhea/colitis	Grade (NCI CTCAE Version 5.0) Grade 2 Recurrent Grade 3 or Grade 4	Action with ANV419 Withhold. Upon resolution to ≤Grade 1, may resume study treatment.	Action with Ipilimumab Withhold. Upon resolution to ≤Grade 1, may resume study treatment.	Corticosteroid and/or Other Therapies Administer corticosteroids (initial dose of 1 to 2 mg/kg prednisone or equivalent) followed by taper.	Monitoring and Follow-Up Monitor participants for continuing signs and symptoms of enterocolitis (ie, diarrhea, abdominal pain, blood or mucus in stool with or without fever) and of bowel perforation (ie, peritoneal signs and ileus). Participants with ≥Grade 2 diarrhea suspected colitis should consider GI consultation and performing endoscopy to rule out colitis. Participants with diarrhea/colitis should be advised to drink liberal quantities of clear fluids. If sufficient oral fluid intake is not feasible, fluid and electrolytes should be substituted via IV infusion.
AST or ALT elevation or increased bilirubin	AST/ALT >3 to 5 × ULN or total bilirubin is more than 1.5 × and up to 3 × ULN AST/ALT >5 × ULN or total bilirubin is more than 3 × ULN	Withhold. Upon resolution to ≤Grade 1, may resume study treatment. Permanently discontinue.	Withhold. Upon resolution to ≤Grade 1, may resume study treatment. Permanently discontinue.	Administer corticosteroids (initial dose of 0.5 to 1 mg/kg prednisone or equivalent) followed by taper. Administer corticosteroids (initial dose of 1 to 2 mg/kg prednisone or equivalent) followed by taper.	Monitor with liver function tests (consider weekly or more frequently until liver enzyme value returned to baseline or is stable).

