### *3.8.2 Clinical Laboratory Tests*

Blood and urine samples for safety analysis of urinalysis, coagulation, chemistry, serology, endocrinology, and hematology parameters (see [Appendix B](#)) will be obtained as specified in the Schedule of Events in the protocol and processed using local laboratory. For purposes of analysis and reporting, laboratory values will be standardized using International System of Units (SI).

Pregnancy tests (serum or urine) will be performed at pre-specified timepoints.

Clinical laboratory evaluations will be summarized using descriptive statistics for continuous laboratory parameters (coagulation, chemistry, hematology, and endocrinology) for the values and changes from baseline at each scheduled visit. The minimum post-baseline value, maximum post-baseline value, and last post-baseline value will also be presented. Both scheduled and unscheduled post-baseline visits will be considered for the summaries of the last, maximum, and minimum post-baseline values.

Categorical serology and urinalysis parameters will be summarized using number and percentage of patients.

Abnormal laboratory results will be graded according to NCI-CTCAE version 5 as applicable. A shift table, presenting the 2-way frequency tabulation for baseline and the worst post-treatment grade according to the NCI-CTCAE grade will be provided for selected clinical laboratory tests when applicable. Both scheduled and unscheduled post-treatment visits will be considered in tabulation of the worst post-treatment grade.

The number and percentage of patients with laboratory abnormalities will be presented for applicable hematology and serum chemistry laboratory parameters.

Additionally, the number and percentage of patients with the following potentially clinically significant abnormal liver function test will be presented:

- ALT  $\geq 3 \times \text{ULN}$ ,  $\geq 5 \times \text{ULN}$ ,  $\geq 10 \times \text{ULN}$ , and  $\geq 20 \times \text{ULN}$
- AST  $\geq 3 \times \text{ULN}$ ,  $\geq 5 \times \text{ULN}$ ,  $\geq 10 \times \text{ULN}$ , and  $\geq 20 \times \text{ULN}$

- Total bilirubin  $\geq 2 \times \text{ULN}$
- Potential Hy's Law cases: ALT or AST  $> 3 \times \text{ULN}$ , total bilirubin  $\geq 2 \times \text{ULN}$ , and ALP  $< 2 \times \text{ULN}$  at the same visit

Clinical laboratory evaluations will also be listed by patient and abnormal values will be flagged.

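### Section 4.4 requires Hy's law patients to stop treatment, but the liver rows of Tables 18 and 19 permit both drugs to resume with no exception for combined enzyme and bilirubin elevation

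*Protocol*

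**What the plan says.** Protocol Section 4.4 lists reasons for stopping study treatment. One bullet reads "Patients who meet Hy's law will be discontinued from treatment". It is not limited to any arm, and the section does not define Hy's law.

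For the combination arms, Section 5.4.5.4 says that for the events listed in the tables "both interventions must be held according to the criteria in Table 18 and Table 19", however the investigator attributes the event. The lower liver row of Table 19 (ipilimumab) is defined as "AST/ALT >3 to 5 × ULN or total bilirubin is more than 1.5 × and up to 3 × ULN". The Grade 2 liver row of Table 18 (pembrolizumab) has the same limits in its footnote when baseline is normal. In both rows the entry for ANV419 and for the partner drug is "Withhold. Upon resolution to ≤Grade 1, may resume study treatment". Permanent discontinuation begins in the next row, at AST/ALT >5 x ULN or bilirubin >3 x ULN.

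The Note under Table 15, in the monotherapy guidance of Section 5.4.5.1, deals with the joint pattern: "Combination of AEs suggestive of drug induced liver injury (DILI), with hepatocellular injury" (AST or ALT >3 x ULN) plus bilirubin >2 x ULN, with no initial biliary obstruction and nothing else to explain it. This "should lead to permanent discontinuation from treatment".

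SAP Section 3.8.2 has its own entry, beginning "Potential Hy's Law cases: ALT or AST": ALT or AST >3 x ULN, bilirubin >=2 x ULN and ALP <2 x ULN at one visit.

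**The concern.** Section 4.4 names Hy's law without limits, and the Table 15 Note gives limits without the name. Tables 18 and 19 treat transaminases and bilirubin as alternatives in one row and never address both together. A site working from the table alone could hold both drugs, see recovery to Grade 1, and restart two agents in a patient whom Section 4.4 says will be discontinued.

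What is at stake is the consistency of a safety stop. The same laboratory picture could lead to discontinuation at a site that starts from Section 4.4 and to re-exposure at a site that starts from the table. The differing limits also mean that the cases tabulated under SAP 3.8.2 need not be those that the protocol's rule is meant to catch.

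**Working it through.** The plan states no figure to reproduce. The check is a side-by-side reading and an intersection of threshold bands, with normal baseline values.

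**1. Inputs**
- Resumable row (Table 18 Grade 2; Table 19 lower row): AST/ALT >3 to 5 x ULN, or bilirubin >1.5 to 3 x ULN.
- Table 15 Note: AST or ALT >3 x ULN and bilirubin >2 x ULN, no initial obstruction, no other explanation.
- SAP 3.8.2: ALT or AST >3 x ULN, bilirubin >=2 x ULN, ALP <2 x ULN.

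**2. Intersection**
- AST/ALT: >3 to 5 combined with >3 gives >3 to 5 x ULN.
- Bilirubin, Table 15 Note: >1.5 to 3 combined with >2 gives >2 to 3 x ULN.
- Bilirubin, SAP: >1.5 to 3 combined with >=2 gives 2 to 3 x ULN.

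The overlap is not empty under either definition.

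**3. Worked case.** Take ALT 4 x ULN, bilirubin 2.5 x ULN, ALP <2 x ULN, no obstruction and no other cause. Since 4 > 3 and 2.5 > 2, both definitions are met and Section 4.4 calls for discontinuation. Since 4 does not exceed 5 and 2.5 does not exceed 3, neither value reaches the permanent-discontinuation row. Both values sit in the row that lets both drugs resume.

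**4. Comparison with Table 15.** Its Grade 2 bands are the same (AST/ALT >3 to 5, bilirubin >1.5 to 3 x ULN), and its action is also to withhold and then continue. There the Note takes the joint pattern out of the row. Tables 18 and 19 have no such note and no reference to Section 4.4 or Table 15.

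**5. Does other text close the gap?**
- Section 5.4.5.4 sends combination events to Section 5.4.5 only when they are clearly attributable to ANV419, and only for the ANV419 action. The same section says that attribution to one component is likely to be difficult.
- Its general rule for discontinuing both drugs starts at Grade 3, above this band.
- Its 42-day limit on holding removes slow recoveries, so the conflict remains for patients who recover to Grade 1 or less within that time.
- No text states which passage takes precedence.

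**6. Abnormal baseline.** Table 18 then grades by multiples of baseline. With a baseline AST of 2 x ULN, for example, Grade 2 runs from 3 x 2 = 6 to 5 x 2 = 10 x ULN. Table 9 admits patients with liver metastases at up to 5 x ULN, so the resumable enzyme band of Table 18 can lie well above 5 x ULN.

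**The case against.** A reader might infer that the protocol gives two opposite commands. It does not. The table rows give a permission, so a site that discontinues breaches neither passage. The requirement in Section 5.4.5.4 governs holding the drugs, not restarting them. The lead-in to the Section 4.4 list is itself permissive ("Discontinuation of a patient from study treatment may occur or any of the following reasons"), although the Hy's law bullet is not. The defect is a missing exception, and that much of the objection stands.

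A reader might also take the whole band to be in conflict. Only cases without obstruction or another cause are, on the Table 15 Note; the SAP definition requires ALP <2 x ULN.

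Nor is the joint pattern ignored elsewhere. Appendix B requires daily PT/INR in any patient with ALT or AST >=3 x ULN and bilirubin >=2 x ULN. SAP 3.8.1.1 lists drug-induced liver injury as a type of dose-limiting toxicity for Part 2. The toxicity criteria in protocol Section 3.1.4 are blacked out, so a further liver definition for that part cannot be excluded. None of this changes the visible wording of the liver rows.

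It is tempting to estimate how many patients would be affected. In ANV419-001, related increases in ALT, AST and bilirubin of any grade each occurred in 6 of 34 patients (18%), but the overlap is not given. Section 5.4.5.1 says that the transient enzyme rises seen with ANV419 typically occur without raised bilirubin. No rate can be derived.

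A claim that discontinuation rates would not be comparable between arms is also unsupported. Arms B and C share these ULN limits when baseline is normal, SAP 3.1.4 plans no formal testing, and SAP 3.8 summarizes safety separately by part.

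**Conclusion.** The inconsistency is real and narrow. With normal baseline values, a combination patient with AST/ALT >3 to 5 x ULN and bilirubin >2 to 3 x ULN (from 2 x ULN on the SAP limit), without obstruction or another cause, is subject to a mandatory stop in Section 4.4 and a permission to resume both drugs in Table 18 or 19. The protocol makes the exception for the matching band in Table 15, and that exception reaches combination patients only in part.

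This rests on reading Hy's law in Section 4.4 as the pattern in the Table 15 Note or SAP 3.8.2, because Section 4.4 defines nothing. Those two differ in the bilirubin limit (>2 against >=2 x ULN) and in how obstruction is excluded (clinical explanation against an ALP limit).

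The practical reach is limited. Section 3.1.2 required a substantial amendment before Part 2 could start. SAP Sections 1 and 5 record that the trial stopped after Part 1 and that the analyses of Parts 2 and 3 will not be performed. No Part 1 result is affected. The point concerns the protocol text and any reuse of these tables.

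**What to change.** State one numeric Hy's law definition in Section 4.4, including how obstruction and other causes are handled. Align the Table 15 Note and SAP 3.8.2 with it. Add a cross-reference to Section 4.4 in the liver rows of Tables 18 and 19 for combined transaminase and bilirubin elevation, so that the row and Section 4.4 agree, and say whether the definition uses multiples of ULN or of baseline when baseline is abnormal. The passages must be reconciled; which action and limits apply is for the sponsor and the Safety Review Committee.

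The cost is a few lines of protocol and SAP wording, with no new tests, visits or data. The amendment required before Part 2 would have been the natural place for it.
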